1) **Title:** The Effect of oral PhenazopyrIdine on Perioperative voiding After mid-urethral sliNg (EPIPhANy study)

2) IRB Review History*

N/A

3) Objectives*

- a) Primary objective: Evaluate the effect of phenazopyridine (brand name Pyridium) on immediate postoperative voiding function in patients undergoing midurethral slings
- b) Secondary objective: Evaluate percent pain reduction with and without use of oral Pyridium at two hours post-procedure.

4) Background*

The midurethral sling (MUS) is a very common, highly successful procedure for the management of stress urinary incontinence due to urethral mobility, with cure rates ranging from 80 to 86%. A common complication of the MUS procedure is short-term postoperative voiding dysfunction. Approximately 20% (7) of patients undergoing MUS are unable to void in the immediate postoperative period and are discharged home with indwelling bladder catheter for 3-5 days. Virtually all patients discharged with a catheter are able to effectively void within 5 days of the procedure and long-term voiding dysfunction is extremely uncommon

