A secondary analysis of a recent study at UMass examining the effect of local anesthetic on postop voiding function showed a potentially dramatic effect of oral phenazopyridine on reducing postoperative voiding dysfunction. During the study, a medication used to dye the urine blue to assess for ureteral injury became briefly unavailable commercially. As a result, we preoperatively gave all patients Pyridium because it has the side effect of dying the urine orange. This allowed us to evaluate the flow from the ureters if needed. This transition occurred in the middle of the study and at the conclusion, we observed that the rate of voiding dysfunction decreased from approximately 28% in those not receiving pyridium to 10% in those receiving pyridium. Because the study was not designed to study this serendipitous finding, we propose to formally assess the validity of this observation. Other than our study, there are no other publications that demonstrate that phenazopyridine may have an effect on postoperative short-term voiding dysfunction. At this time there is no evidence of adverse effect to denying patients phenazopyridine. Because of the nature of our surgical practice, many of the procedures we perform have the risk of ureteral injury and we made a decision to give this medication preoperatively to all of our patients. In the 15 years that the PI has practiced, we have never seen a ureteral injury in a patient undergoing a midurethral sling. The documented risk of injury to the lower urinary

Page 1 of 10

tract during anti-incontinence surgery is approximately 2.6%, with all of these injuries being to the bladder or urethra and 0 ureteral injuries in 351 cases. There is no place for phenazopyridine in the management or assessment of injuries to the bladder or urethra and many providers at UMass and other institutions in the US do not give phenazopyridine to their patients undergoing a midurethral sling. Phenazopyridine is the only oral medication that is available to evaluate the patency of the ureter after pelvic surgery.

References:

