- 2. Nilson CG Kuuva N, Falconer C, Rezapour M, Ulmsten U, (2001) Long term results of he tension-free vaginal tape (TVT) procedure for the vaginal treatment of female stress incontinence. Int Urogynecol J Pelvic Floor Dysfunct 12(Supple. 2): S5-8.
- 3. Voiding function after Mid-Urethral Slings with and without local anesthetic: Randomized Controlled Trial. UMass IRB H-14197

5) Inclusion and Exclusion Criteria*

Inclusion criteria:

1. Any female subjects scheduled to undergo Mid-Urethral Sling (MUS) through the UMass urogynecology service for incontinence.

Exclusion criteria:

- 1. Planned concurrent prolapse or other procedure besides cystoscopy
- 2. Using intermittent self catheterization preoperatively
- 3. Undergoing spinal anesthesia for the procedure
- 4. Known allergy to phenazopyridine (AKA Pyridium)
- 5. Renal insufficiency
- 6. Any condition or situation that in the attending physician's opinion would contra-indicate the use of phenazopyridine
- 7. Subjects not competent to give consent
- 8. Prisoners
- 9. Non-English or non-Spanish speaking patients
- 10. Age < 18
- 11. Pregnant patients
- 12. Contraindications to the use of IV methylene blue including
 - a) Patients with known hypersensitivity reactions

Page 2 of 10 Revised: 6/30/16 Approved 7/7/16

- b) Severe renal insufficiency
- c) Patients with G6PD deficiency

6) Study-Wide number of Subjects*

N/A not a multicenter study

7) Study-Wide Recruitment Methods*

N/A not a multicenter study

8) Study Timelines*

- Participants will be enrolled in the study for approximately 6 weeks.
- We anticipate 2 years to enroll all the subjects into the study
- Primary analysis will be completed within 6 months after enrollment is completed.

9) Study Endpoints*

- Primary outcome is the rate of voiding dysfunction between the two groups.
- Secondary outcomes include: complications, perioperative pain scores,
- Once 50% of the subjects have completed their procedures, we will perform an interim analysis of the rates of voiding dysfunction. If there is a statistically significant difference (p<0.01) at this interval analysis, we will terminate the study.

10) Procedures Involved*

Study design and randomization

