The Mid Urethral Sling will be performed in standard fashion based on manufacturer's recommendations and instructions to minimize inter-observer variations. We will perform the procedure according to our usual and customary techniques. The subject will receive the same technique and interventions that a routine patient on the Urogyn service would expect to undergo. There will be no changes to the technique for the purpose of the study.

Bladder challenge:

Patient will undergo voiding trial at same day surgery per our usual and customary protocol. This is the same protocol the subject would undergo as a patient on the Urogyn service. The bladder challenge will be interpreted in our usual manner and the subject managed according to our routine clinical protocols.

Postoperative care:

Subjects will undergo routine postoperative care and followup. Subjects failing their bladder challenge will be seen in the Urogyn clinic according to routine clinical protocols and data councerning their void trials collected. Subjects will undergo routine followup evaluation 6 weeks postoperatively in the order to assess any potential long-term voiding dysfunction. Information on any postoperative complications will be collected

Administration of Visual analog scale:

Page 4 of 10 Revised: 6/30/16 Approved 7/7/16

- (1) Visual analog scale for assessment of pain will be administered at two time intervals.
 - (a) VAS #1) Preoperative VAS will be done by the principal investigator or any of the study assistants. The VAS form will be part of subject's packet.
 - (b) **VAS#2)** VAS will be administered by one of the study investigators 2 to 3 hours after the surgical procedure in the SACU.

11) Data and Specimen Banking*

N/A

12) Data Management*

Power Calculation: We used data from the recent "*Urine and Me*" study conducted at UMass. A 20% percent difference in subjects passing the bladder challenge was felt to be clinically significant. In order to capture this difference a power calculation was performed via the Wilcoxon signed-rank test. Based on this, to detect a 20% difference with a α -error = 0.05 and a power (1- β error) = 0.80, a minimum of 41 subjects per group (82 total) will need to be recruited. Assuming ~ 10% dropout rate (8), we will seek to recruit 90 patients.

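### The 80% power stated for 41 per group is not delivered at the local failure rates in Section 4, and Section 12 gives no rates from which it could be checked

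*Combined protocol and SAP*

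**What the plan says.** Section 4 (Background) gives the reason for the trial. In an earlier local study, "the rate of voiding dysfunction decreased from approximately 28% in those not receiving pyridium to 10% in those receiving pyridium". That comparison was unplanned, and the protocol says: "Because the study was not designed to study this serendipitous finding, we propose to formally assess the validity of this observation". Section 4 also gives a general background figure: "Approximately 20% (7) of patients undergoing MUS are unable to void in the immediate postoperative period".

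Section 9 makes the outcome binary: "Primary outcome is the rate of voiding dysfunction between the two groups".

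Section 12 (Data Management, Power Calculation) takes its inputs from an earlier local study and states: "A 20% percent difference in subjects passing the bladder challenge was felt to be clinically significant". It continues: "In order to capture this difference a power calculation was performed via the Wilcoxon signed-rank test". The result is given as: "to detect a 20% difference with a α -error = 0.05 and a power (1- β error) = 0.80, a minimum of 41 subjects per group (82" in total. Ninety are to be recruited to allow for about 10% dropout. Section 12 gives no control rate, no treated rate, no sidedness for alpha, and no reason for a target above the effect reported in Section 4. Its data analysis paragraph names the unpaired t test and analysis of covariance, but no method for comparing two proportions.

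**The concern.** The power of a comparison of two proportions depends on both rates, not only on the gap between them. A 20-point difference needs far fewer patients when one rate is close to zero than when the rates are 28% and 8%. Without the rates, the 80% cannot be verified.

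The target is also slightly larger than the effect under test: 28 − 10 = 18 points, against 20. Both features make the stated power look better than it is for the Section 4 observation. A reader of a non-significant result would take the trial to have had a four-in-five chance of detecting the effect, when the chance was nearer one in two. A null finding could then be read as refuting the earlier observation on weaker evidence than the protocol implies.

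**Working it through.** **Inputs.** Untreated failure 28% and treated failure 10% (Section 4); background failure 20% (Section 4); difference 20 points, alpha 0.05, power 0.80, 41 per group, 90 recruited (Section 12); 1:1 allocation (Section 10). Two-sided testing is my assumption; one-sided results are shown where they matter. All figures are for a single final analysis and ignore the interim look in Section 9.

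**Formula.** With p̄ the mean of p1 and p2, the number per group is

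n = [1.96·√(2p̄(1−p̄)) + 0.8416·√(p1(1−p1) + p2(1−p2))]² / (p1−p2)²

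**Step 1: try to reproduce 41 for a 20-point difference.**

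| Failure rates | n per group, two-sided | n per group, one-sided |
|---|---|---|
| 20% v 0% | 35 (44 with continuity correction) | 27 |
| 22% v 2% | 41 | 32 |
| 26% v 6% | 52 | 41 |
| 28% v 8% | 57 | 45 |
| 30% v 10% | 62 | 49 |

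The stated 41 appears only at rates such as 22% v 2% (two-sided) or 26% v 6% (one-sided), which the documents do not give. A one-sample signed-rank calculation with a standardised shift of about 0.45 also gives 41, but no such shift is stated. So the figure is not reproduced from the documents' rates.

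**Step 2: number needed at the documents' local rates.**

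- 28% v 10%: p̄ = 0.19; √(2×0.19×0.81) = 0.5548; √(0.2016 + 0.0900) = 0.5400. n = (1.0874 + 0.4545)² / 0.0324 = 73.4, so 74 per group (148 in total).
- 28% v 8%: p̄ = 0.18; √(2×0.18×0.82) = 0.5433; √(0.2016 + 0.0736) = 0.5246. n = (1.0649 + 0.4415)² / 0.04 = 56.7, so 57 per group.

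**Step 3: power with the planned numbers.** Exact power sums the binomial probabilities of every pair of failure counts for which the test gives p ≤ 0.05, two-sided. The normal approximation is Φ[(|p1−p2|·√n − 1.96·√(2p̄(1−p̄))) / √(p1(1−p1) + p2(1−p2))].

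| Rates | n per arm | Normal approx. | Exact, chi-square | Exact, Fisher |
|---|---|---|---|---|
| 28% v 10% | 41 | 55% | 57% | 47% |
| 28% v 10% | 45 | 59% | 62% | 49% |
| 28% v 8% | 41 | 66% | 69% | 59% |

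A one-sided 0.05 test with 41 per arm gives 67% for 28% v 10% and 77% for 28% v 8% (normal approximation), both still below 80%.

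**Step 4: the background rate.** From 20%, a 20-point gain means 20 − 20 = 0% failing on pyridium. At 20% v 0%, 41 per arm gives about 87% power (Fisher 86%). This is the one pair built on a Section 4 rate at which 80% is met, and it requires no failures at all in an arm where Section 4 reports 10%.

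**The case against.** **The gap is small and the rates are approximate.** This is fair: 29.5% v 9.5% would be exactly 20 points, so rounding could close the 2-point gap. It does not restore the power, since 29.5% v 9.5% needs 61 per group.

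**The 20% might be relative.** The text does not say, and 72% to 90% passing is a 25% relative gain. But no relative reading tried gives 41: 72% v 86.4% passing needs 124 per group, 80% v 96% passing needs 64, and 28% v 22.4% failing needs 943. The absolute reading is also the more natural one.

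**Clinical importance is a judgement and need not match a preliminary estimate.** This stands. Lowering the mark to 18 points because 18 was observed would derive importance from an unplanned result. Nothing here asks for that.

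**A stronger reading is tempting:** that a faithful replication would fail the trial's own threshold. The documents do not support it. Section 12 uses 20 points only for sizing, and no rule for success, reporting or stopping refers to it; the interim rule in Section 9 is p<0.01. An observed gap below 20 points can be significant: 11/41 v 4/41 is 17.1 points with p = 0.046 by the uncorrected z test, though Fisher gives 0.084. It is true that at 28% v 10% the observed difference reaches 20 points only 37% of the time with 41 per arm. That is mostly generic, because a mark of 18 points would be reached only 48.5% of the time. With 45 per arm both marks are reached 45.5% of the time, since each needs a gap of 9 subjects.

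**A reader might also infer that 20 points is unattainable**, because Section 4 puts failure at about 20%. That is a general background rate. The local untreated rate is about 28%, from which 28% v 8% is possible.

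**Conclusion.** The point holds as one about stated power. Section 12 claims 80% with 41 per group and gives no rates. At the local rates in Section 4, power is about 57% (Fisher 47%) for the 18-point effect under test, and about 69% (Fisher 59%) if the full 20-point difference is measured from 28%. Full retention of 90 raises the first figure only to about 62% (Fisher 49%).

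This rests on an absolute reading of the 20%, two-sided testing at 0.05, independent arms, and the approximate 28% and 10% taken at face value. The inputs behind the Section 12 calculation are not in the documents, so an unstated pair of rates such as 22% v 2% could have produced 41; if so, it needs to be stated. The choice of 20 points is not itself an error, and an 18-point result would not be a failed trial. Naming a paired test for two independent groups with a binary outcome is a separate fault.

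**What to change.** In Section 12:

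1. State the pair of failure rates assumed: 28% v 10% as the observation under test, and 28% v 8% as well if the 20-point target is kept.
2. Replace the 80% figure with the power that 41 per group gives for those rates by a two-proportion method, naming the test and its sidedness. By two-sided chi-square these are about 57% and 69%; by Fisher, about 47% and 59%.
3. State that the primary result will be reported as the risk difference with its 95% confidence interval, so that a non-significant result is read with its precision.

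Keep 90 subjects. The cost is protocol wording and a less favourable stated power, with no extra patients and no change to procedures. Restoring 80% for 28% v 10% would take 148 evaluable subjects, or 165 recruited at 10% dropout (148/0.9 = 164.4). That is a separate decision and is not asked for here.

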This study is a randomized controlled trial. Randomization will be performed using software and a block randomization scheme. Study assignment will be completed using sequentially numbered sealed opaque envelopes. All the research procedures described other than the use or not of phenazopyridine will be applicable to both arms of the study. Subjects will have a 50% chances of getting either phenazopyridine or nothing.

Because pyridium turns the urine orange, it is impossible to blind the patients and researchers to the study assignment. Because there is no known placebo that turns the urine orange, there is no value to using an actual placebo tablet. Subjects will be assigned to either receive pyridium or not receive pyridium preoperatively.

Page 3 of 10 Revised: 6/30/16 Approved 7/7/16

Screening potential subjects: Investigators will screen potential subjects for contraindications to methylene blue. Prior obtaining the routine surgical consent for the potential subject's surgical procedure, the patient's medical history in the UMass Electronic Medical Record is routinely reviewed. The medical record will be reviewed for a diagnosis of G6PD and if found, the potential subject will be excluded.

Once written consent has been obtained, subject number will be assigned and the appropriate randomization envelope will be opened. The study assignment will not be formally shared with the subject. Those assigned to the "pyridium" arm will have orders written for the standard 200 mg dose of pyridium to be given on arrival to the Surgical Admissions Care Unit (SACU). Those assigned to the "NO pyridium" arm with have their routine preoperative orders written along with an order for "No preoperative pyridium".

Subjects will then follow the routine perioperative care for their procedures with the only study interventions being the gathering of PHI and performing postoperative pain assessments.

PHI will be obtained at the time of the surgical consent with the purpose to evaluate for possible confounders affecting the postoperative bladder function.

Surgical procedure:

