Data analysis: Continuous measures will be compared using the unpaired Student's t test. Association between outcome measures and graph assignment will be adjusted according to demographic differences using an analysis of covariance. Standard statistical programs (SAS, SPSS) will be used to determine the mean differences between the voided/catheterize and bladder scanner volumes.

13) Provisions to Monitor the Data to Ensure the Safety of Subjects*

There is minimal risk involved with the denial of pyridium to subjects. Prior to the withdrawal of indigo carmine from the market in 2014, patients did not routinely receive pyridium preoperatively. Currently a minority of surgeons use pyridium in sling procedures with most using nothing. In the event that the ureters need to be assessed for patency, subjects will be given methylene blue to dye the urine. This is the intervention currently used to assess ureters in procedures where ureteral patency is assessed. Thus both groups are receiving care that is considered within the standard of care.

Subjects will be monitored in a similar manner to all of our postoperative patients. There is a chance that pyridium may be beneficial to patients and that denying this medication may result in less desirable outcomes. This study is specifically designed to look at the issue. We plan to perform an interim analysis of the data once 50% of subjects have completed the study and if there is a clear benefit (or harm) from this medication, will terminate the study early and offer the medication to all patients.

Page 5 of 10 Revised: 6/30/16 Approved 7/7/16

14) Withdrawal of Subjects*

Subjects are free with withdraw from the study at any time. If subjects withdraw their participation, any data that has already been collected for research purposes will be destroyed or anonymized so that it can no longer be identified with the subject. There should not be additional data collection of demographic information for research purposes at the time a subject withdraws their consent for the study.

15) Risks to Subjects*

This study poses minimal risk to subjects. Subjects randomized to the pyridium arm will receive pyridium as it is commonly given to patients undergoing reconstructive procedures currently through the Urogyn division at UMass. Subjects denied pyridium will undergo the same procedures and techniques that our patients not in the study will receive.

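### The sample size uses a signed-rank test for a two-arm pass/fail outcome; with the protocol's own rates and two-sided alpha, 41 per group gives about 62–66% power for 20 points, not 80%

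*Combined protocol and SAP*

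**What the plan says.** Section 9 (Study Endpoints) defines the outcome: "Primary outcome is the rate of voiding dysfunction between the two groups". Section 10 sets up a parallel 1:1 randomized comparison: "Subjects will have a 50% chances of getting either phenazopyridine or nothing".

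The power calculation in section 12 (Data Management) starts from the effect size, "A 20% percent difference in subjects passing the bladder challenge was felt to be clinically significant", and continues: "In order to capture this difference a power calculation was performed via the Wilcoxon signed-rank test". With alpha 0.05 and power 0.80 it concludes that "a minimum of 41 subjects per group (82 total) will need to be recruited". Eight more subjects for dropout bring the target to 90. The paragraph says its data come from an earlier UMass study, but quotes no rate, standard deviation or sidedness.

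The data analysis paragraph of section 12 says "Continuous measures will be compared using the unpaired Student's t test" and adds an analysis of covariance for adjustment. It names no test for a difference between two proportions.

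Section 4 (Background) gives the only arm-specific rates: about 28% voiding dysfunction without the drug and 10% with it. It also quotes a general rate of about 20% after the procedure.

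**The concern.** The signed-rank test compares paired measurements, or one sample against a fixed value. Here nothing is paired and the outcome is pass/fail, so a sample size from that test says nothing direct about the power of the comparison the trial will make. This part needs no assumption.

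The stated 80% is the whole justification for 82 evaluable subjects. If true power is well below that, a non-significant result is quite likely even when the drug works as hoped, and a reader who trusts the 80% will take it as evidence of no effect. Because no suitable test is named for the primary outcome either, the analysis section does not correct the mismatch.

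**Working it through.** **1. Can 41 be reproduced?** Not from the text, because the signed-rank calculation needs inputs that are not given. Trying two-proportion formulas for a 20-point difference at 80% power:
- Two-sided, pooled: n = 41 requires about 22% v 2%.
- One-sided, pooled: n = 41 requires about 26% v 6%.
- One-sided, unpooled or arcsine, 28% v 8%: n = 43. This is close, but needs a one-sided alpha that the protocol does not state.

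**2. Inputs for the check.** From section 12: n = 41 per group, alpha 0.05, and a difference of 20%, read as absolute points. From section 4: 28% without drug, 10% with drug. A 20-point gap anchored to one of these gives 30% v 10% or 28% v 8%; the observed pair is 28% v 10%. Two-sided alpha is my assumption. Section 13 supports it, since the trial may stop for effects in either direction: "if there is a clear benefit (or harm) from this medication, will terminate the study early". The interim look is left out of these figures.

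**3. Power, pooled two-proportion formula.** With d = p1 − p2 and p̄ = (p1 + p2)/2:

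power = Φ{ [d√n − 1.96√(2p̄(1−p̄))] / √(p1(1−p1) + p2(1−p2)) }, √41 = 6.403

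- 30% v 10%: (1.2806 − 1.1087)/0.5477 = 0.314, power 62.3%
- 28% v 8%: (1.2806 − 1.0649)/0.5246 = 0.411, power 66.0%
- 28% v 10%: (1.1526 − 1.0874)/0.5400 = 0.121, power 54.8%

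The chance of missing the effect is therefore 38%, 34% and 45%, against the planned 20%.

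**4. Sensitivity.**

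| Case | 30 v 10 | 28 v 8 | 28 v 10 |
|---|---|---|---|
| Two-sided, 41 per group, pooled formula | 62.3% | 66.0% | 54.8% |
| Same, exact chi-square | 64.5% | 68.8% | 56.8% |
| Same, exact Fisher | 54.9% | 58.9% | 46.8% |
| Two-sided, 45 per group, pooled formula | 66.5% | 70.1% | 58.8% |
| One-sided, 41 per group, pooled formula | 73.9% | 77.0% | 67.2% |
| One-sided, 45 per group, pooled formula | 77.4% | 80.3% | 70.8% |

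The 45-per-group rows matter because the outcome is measured on the day of surgery ("Patient will undergo voiding trial at same day surgery per our usual and customary protocol"), so losses may be few.

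**5. What would give 80%, two-sided, at 41 per group?** By the pooled formula, 22% v 2% gives 80.8% and 20% v 0% gives 86.9%. A 20-point difference reaches 80% only for a control rate up to 22.3% (23.6% at 45 per group). From a 28% control rate, the drug rate must fall to 5.3%.

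**6. Sample size for 80%, two-sided.** n per group = [1.96√(2p̄(1−p̄)) + 0.8416√(p1(1−p1) + p2(1−p2))]² / d²

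- 30% v 10%: (1.1087 + 0.4610)²/0.0400 = 61.6, so 62 (124 total)
- 28% v 8%: (1.0649 + 0.4415)²/0.0400 = 56.7, so 57 (114 total)
- 28% v 10%: (1.0874 + 0.4545)²/0.0324 = 73.4, so 74 (148 total)

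**7. Precision.** The 95% CI half-width for the risk difference at 28% v 10% is 1.96 × √((0.28×0.72 + 0.10×0.90)/41) = 0.165, about 16.5 points.

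**The case against.** The strongest reply is that 62–66% is not a recomputation of the sponsor's figure. The inputs came from a study we cannot see, the anchors are taken from the Background, and two-sided power at 41 per group runs from 55% to 87% depending on the rates assumed. The 10% on drug came from a non-randomized, mid-study switch, so it does not exclude a lower rate, and the general 20% rate would permit a favourable case. This stands as a limit: the power figure is conditional. It does not rescue the 80%, because the plan states no rates that would support it, and the rates that would do so put failure on drug well below the only value the protocol reports.

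The figures also depend on the formula, and this stands too. Exact chi-square power is two to three points higher at the anchored rates. It is clearly higher at the favourable end: 89% for 22% v 2% and over 97% for 20% v 0%. The control-rate limit moves from about 22% to about 24%, and the required fall from 28% ends at about 6% rather than 5%. Fisher's test is lower throughout. None of these reaches 80% at the anchored rates.

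Two smaller points change nothing. If signed-rank is a slip for rank-sum, 41 per group still falls short with these anchors at two-sided 0.05. If 20% was meant as a relative difference, then from a 72% pass rate it is 0.20 × 72 = 14.4 points, and power is lower still.

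**Conclusion.** The concern holds. The test named for the sample size does not fit the design or the outcome, its inputs are missing, and no suitable test is named for the primary analysis; none of this depends on an assumption. Under two-sided alpha 0.05, an absolute 20-point difference and an arm anchored at 28% or 10%, 41 per group gives 62–66% power by the pooled formula (64–69% by exact chi-square), not 80%. For the observed 28% v 10% it is 55–57%. With these anchors, the pooled formula reaches 80% in only one corner: 28% v 8%, one-sided, with all 90 evaluable. This must be fixed before the stated power is relied on.

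**What to change.** In the power calculation of section 12, replace the signed-rank sentence with a two-sided comparison of two independent proportions, for example a chi-square test. State the assumed control rate, that 20% means absolute points, the sidedness of alpha, and the formula used. Name the same test for the primary outcome in the data analysis paragraph.

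Keep 90 subjects and restate the power at 41 per group (pooled formula): about 62% for 30% v 10%, 66% for 28% v 8%, 55% for 28% v 10%, and 80% from a 28% control rate only for a fall to about 5%. The 45-per-group figures (66%, 70%, 59% for the first three) can be added if little loss is expected. Say that the primary result will be reported as a risk difference with its 95% CI (half-width about 16.5 points at 28% v 10%), so that a non-significant result is not read as absence of effect.

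This costs wording only and no extra patients. It does not raise the power; it makes the stated power honest. If the sponsor wants to keep 80%, the alternative is 114–124 evaluable for 20 points, or 148 for 28% v 10%. At the protocol's ratio of 90 recruited to 82 evaluable, that is about 126–137 or 163 recruited. At 90 in 2 years (45 a year), enrollment would take about 2.8–3.0 or 3.6 years.

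### Section 13 attaches the offer of phenazopyridine to every patient to an interim finding of harm as well as benefit; this is almost certainly a drafting slip, and the offer should follow benefit only.

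*Combined protocol and SAP*

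**What the plan says.** Two places in the combined protocol and SAP deal with the interim look.

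- Section 9 (Study Endpoints) plans an interim analysis of voiding dysfunction rates at half-way and gives the rule: "If there is a statistically significant difference (p<0.01) at this interval analysis, we will terminate the study". It states no direction and no action on the drug.
- Section 13 (Provisions to Monitor the Data to Ensure the Safety of Subjects) returns to the same look: "We plan to perform an interim analysis of the data once 50% of subjects have completed the study". It then gives the consequence: "if there is a clear benefit (or harm) from this medication, will terminate the study early and offer the medication to all patients".

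The reason offered in Section 13 runs in one direction only: "There is a chance that pyridium may be beneficial to patients and that denying this medication may result in less desirable outcomes". That fits Section 4, where the observation behind the trial is that "the rate of voiding dysfunction decreased from approximately 28% in those not receiving pyridium to 10% in those receiving pyridium".

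**The concern.** The Section 13 sentence has one condition with two alternatives, benefit or harm, and one joined action: stop, and offer the drug. Nothing in the grammar limits the second half of the action to the first alternative. Taken at its word, the protocol responds to evidence that the drug harms patients by offering it to all of them.

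This is the safety-monitoring section, and the sentence is the only one that says what happens to the drug after an interim stop. Anyone following the protocol to the letter would have the wrong instruction in the one situation that a harm rule exists to cover.

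**Working it through.** The point concerns the wording of a decision rule. The plan states no figure to reproduce, so the check is mainly a reading of the two sections side by side.

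**Step 1: what each section prescribes.**

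| Interim finding | Section 9 | Section 13, as written | Evident intent |
|---|---|---|---|
| Clear benefit | Stop | Stop; offer drug to every patient | Same as written |
| Clear harm | Stop | Stop; offer drug to every patient | Stop; no offer |
| Neither | Continue (implied) | Continue (implied) | Continue |

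Only the Section 13 harm cell is wrong. Section 9 agrees with it on stopping and is silent on the drug, so it does not correct it.

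**Step 2: is there a correction elsewhere?** The word 'harm' occurs once in the document, in this sentence. 'Terminate' occurs twice, in Sections 9 and 13. No other section gives an action for the drug after harm. The sentence is complete as printed, with no redaction or broken table that could hide a qualifier.

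**Step 3: which reading was meant?** The preceding sentences of Section 13 concern the risk of withholding a useful drug, and the expected effect is benefit. The offer follows naturally from benefit. The words in parentheses look like an addition to a sentence written for benefit, meant to widen the reasons for stopping.

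**Step 4: how likely is the harm direction to be reached?** This is context only; the wording is wrong whatever the answer.

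Inputs:
- Half of the 90 subjects in Section 25 is 45, split as 22 on drug and 23 off.
- The threshold is p<0.01 (Section 9).
- Rates of 10% on drug and 28% off come from Section 4. The equal rates of 20% are an assumption, as is the reversed scenario.
- The test is an assumed two-sided Fisher exact test, since the protocol names none for the interim.

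With x failures of 22 on drug and y of 23 off,

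P(stop for harm) = Σ Bin(x; 22, p_drug) × Bin(y; 23, p_off),

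summed over all (x, y) with Fisher p<0.01 and x/22 > y/23. P(stop for benefit) is the same sum over x/22 < y/23.

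| True rate on drug / off | P(stop for benefit) | P(stop for harm) |
|---|---|---|
| 10% / 28% (Section 4) | 0.098 | 0.00001 |
| 20% / 20% | 0.003 | 0.004 |
| 28% / 10% (reversed) | 0.000006 | 0.13 |

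Taking half of 82 instead (20 on drug and 21 off) gives P(stop for harm) of 0.00002, 0.004 and 0.11 for the three rows. The conclusion is the same.

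**Step 5: what changes when the sentence is corrected?** Only the action after harm. The timing of the look, the threshold, the sample size, alpha and power all stay as they are.

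**The case against.** The strongest reply is that this is copy-editing. An ordinary reader takes the parenthesis to widen the stopping trigger and understands the offer to follow benefit. No analysis, estimate or conclusion depends on it. The harm direction is also close to unreachable under the trial's own premise, so calling the rule wrong in one of two directions could suggest that the two are comparably likely. They are not, as Step 4 shows. The exposure is also slight: subjects in the drug arm "have orders written for the standard 200 mg dose of pyridium to be given on arrival", a single dose before surgery.

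Most of this stands, and it sets the point at the lowest severity. It does not make the sentence right. This is a stated decision rule in safety text, and the harm direction matters chiefly when the drug does harm, where the chance of reaching it is about 0.13 in the reversed scenario.

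Three stronger readings are tempting, and the documents do not support them.

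- A reader might infer that harm here includes complications, since Section 10 says "Information on any postoperative complications will be collected". But Section 9 ties the interim analysis to voiding dysfunction, and no section sets a stopping rule for complications. Section 13 speaks more loosely of the data, but most naturally means the same look.
- A reader might want to count the subjects who would be exposed after a harm stop. The documents give no interval between consent and surgery, and a count of outstanding study orders would not measure this error, which lies in the offer.
- A reader might conclude that the drug should be barred altogether after a harm finding. Section 4 describes giving it preoperatively so that flow from the ureters can be seen, and Section 32 treats that use as standard care. A voiding signal in patients having a sling alone (Section 5 excludes other concurrent procedures except cystoscopy) would not settle that wider question.

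**Conclusion.** The point holds as an error of wording. As written, Section 13 prescribes offering the drug to every patient after clear harm, and no other section corrects it. That it is a slip is an inference, but a well-supported one; nothing suggests that the investigators mean to give a drug found harmful. Stopping in either direction is appropriate and is not questioned.

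The size is small: one misattached action, in a direction very unlikely to be reached under the planned effect. The probabilities rest on the assumed Fisher test and an even split at half-way; the reading of the sentence rests on neither. It is worth correcting at the next opportunity, and nothing in the design or analysis has to be reconsidered because of it.

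**What to change.** Replace the sentence in Section 13 with wording to this effect: *If the interim analysis shows clear benefit or clear harm, the study will stop early. After clear benefit, phenazopyridine will be offered to every patient. After clear harm, no further study doses will be given.*

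Limiting the harm clause to study doses leaves clinical use of the drug to assess the ureters outside the trial untouched. Section 9 needs no change for this point.

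The cost is one sentence in a protocol amendment, with no extra data, staff or subjects.
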